#### 7. INVESTIGATIONAL PLAN

#### 7.1 OVERALL STUDY DESIGN

This is a feasibility, multi-center, open-label, non-significant risk device study recruiting up to approximately 45 healthy, sexually active women who are not at risk for pregnancy due to previous female tubal sterilization, and their male partners, with the goal of approximately 25 couples completing the study. Each woman will be seen for a screening visit and in 5 scheduled menstrual cycles:

- One baseline PCT cycle (no device) with one act of intercourse at the time of ovulation to collect baseline information on the female and male participants (enrollment will take place at the successful completion of this cycle);
- One Caya PCT cycle using the Caya diaphragm with spermicide during one act of intercourse at the time of ovulation
- One Ovaprene™ safety, release, acceptability, and fit assessment cycle with no acts of intercourse (abbreviated as "Ovaprene™ safety cycle"); and
- Two Ovaprene™ PCT cycles using Ovaprene™ during one act of intercourse at the time of ovulation in each cycle.

The purpose of the Caya PCT cycle is to ensure that in this study population and at these sites, results that are expected to be observed in a PCT cycle with an approved vaginal barrier can be replicated.

Participants will be seen in 21 scheduled visits over a period of up to 6-7 months, as shown below, and will be contacted 7-10 days after the final visit. (Additional visits may take place if certain procedures must be repeated.)

Table 3 Study Visits and cycles (following Visit 1)

	Cycle Base	e 1 line P	СТ	Cycle Caya	e 2 PCT	, , , , , , , , , , , , , , , , , , , ,										Cycle Ovap	e 5 orene"	™ PCT		
Visit	2	3	4	5	6	7	8	9	10	11	12	13	14	15	16	17	18	19	20	21
	BP1	BP2	BP3	CP1	CP2	OS1	OS2	OS3	OS4	OS5	OP1	OP2	OP3	OP4	OP5	OP1	OP2	OP3	OP4	OP5

Many of the PCT and safety aspects of this study design are based on two previous studies:

- A PCT study of the SILCS diaphragm, now referred to as Caya, used with 2% N-9 or a personal lubricant, described in Schwartz, et al, 2008.
- A PCT study of the SILCS diaphragm, now referred to as Caya, used with 3% N-9, ContraGel, or no gel, described in Mauck, et al, 2017 8

#### 7.2 ANTICIPATED LENGTH OF STUDY

Each subject's participation will last 6-7 months. Cycles may need to be repeated; thus, participation for some women may be more than 7 months.

#### 7.3 NUMBER OF SUBJECTS

Approximately 45 women will be enrolled with the goal to have approximately 25 participants complete the trial. Subjects who discontinue early may be replaced.

Version: 06.00 (FINAL) Date: June 13, 2019

#### 7.4 TREATMENT ASSIGNMENT

This is an open-label study in which all participants will use the same study product, thus no treatment assignment will take place.

#### 7.5 CRITERIA FOR PARTICIPANT DISCONTINUATION

Each participant will be informed of her and her partner's right to withdraw from the study at any time and for any reason. A participant may be discontinued from study treatment at any time if the participant, the Investigator, or the Sponsor feels that it is not in the participant's best interest to continue on study.

Participants who sign the informed consent and agree to participate in the study, but do not meet eligibility criteria will be considered screen failures.

Following enrollment, participants may be discontinued from the study for the following reasons:

- Failure to follow protocol requirements that is judged severe enough by the investigator to significantly affect study outcomes or requires discontinuation of study treatment
- Having an average of >5 progressively motile sperm per HPF in the cervical mucus 2-3 hours after intercourse using a Caya diaphragm with nonoxynol-9 if the result was clearly the result of the participant not using or inserting the diaphragm properly.
- Adverse event, including diagnosis of symptomatic bacterial vaginosis (BV) or an STI (in the
  participant or her partner), or any intercurrent illness that would jeopardize the participant's health
  or the interpretation of the results of the study. (An outbreak of genital herpes or condylomata
  would require discontinuation.)
- Pregnancy
- Loss to follow-up
- Participant withdrawal of consent
- Sponsor decision to discontinue trial

Prior to discontinuing a participant from the study, the site should contact Daré or designee. The reason for discontinuation must be recorded on the appropriate section of the participant's CRF.

Version: 06.00 (FINAL) Date: June 13, 2019

#### 8. SELECTION AND WITHDRAWAL OF SUBJECTS

The volunteers for this study will be recruited through various methods, including existing databases (as protected health information permits) and through advertisements in local media outlets which have been approved by the local Institutional Review Board (IRB).

Only women will be recruited since Ovaprene™ can only be used by women and the endpoints require genital sampling. Although the National Institutes of Health (NIH) has mandated that children, defined as younger than 21 years old, be included in research trials when appropriate, this study fits one of the "Justifications for Exclusion" as set forth by the NIH. Specifically, "insufficient data are available in adults to judge potential risk in children" and "children should not be the initial group to be involved in research studies." We will recruit female participants aged 18 to 50 years who can legally provide informed consent. Efforts will be made by the sites to recruit participants so that the racial, ethnic, and parity characteristics of the subject population will reflect the demographics of the study sites. No selection criteria shall be based on race or ethnicity.

Note: Volunteers must meet all the following inclusion criteria and none of the exclusion criteria prior to enrollment (which takes place at successful completion of the Baseline PCT Cycle):

#### 8.1 INCLUSION CRITERIA

- 1. Women aged 18-50 years, inclusive
- 2. General good health, by volunteer history and per investigator judgment
- 3. History of regular menstrual cycles of 24-35 days (inclusive), by volunteer report
- 4. History of Pap tests and follow-up consistent with standard medical practice or willing to undergo a Pap test at Visit 1.
- 5. Protected from pregnancy by female tubal sterilization
- 6. Willing to abstain from or engage in intercourse with and without condoms and to abstain from other vaginal activitya as required in the protocol
- 7. In a mutually monogamous relationship for at least the last four months with a male partner who:
  - a. Is at least 18 years old;
  - b. Has no known risk for STIs;
  - c. Is willing and able to comply with protocol requirements including sexual activity/ abstinence and condom use requirements; and
  - d. Can engage in vaginal intercourse with the participant, with and without condoms, as specified in protocol
- 8. Vaginal and cervical anatomy that, in the opinion of the investigator, lends itself to easy colposcopy and genital tract sample collection
- 9. Willing to give voluntary consent, sign an informed consent form and comply with study procedures as required by the protocol

<sup>a "Other vaginal activity" includes insertion of vaginal medications/products other than the study product (prescription or over-the-counter), as well as insertion of sex toys, fingers, or anything else into the vagina. Tampons may be used during all days of menses in the Baseline PCT and Caya PCT cycles, but only during the first three days of menses in Ovaprene cycles.

Version: 06.00 (FINAL) Date: June 13, 2019

#### 8.2 EXCLUSION CRITERIA

- 1. History of hysterectomy
- 2. Vasectomy in male partner
- 3. Sterility or known history of sperm dysfunction in male partner
- 4. Within two calendar months from the last pregnancy outcome. Note: If recently pregnant must have had at least two spontaneous menses since pregnancy outcome.
- 5. Current use of any hormonal contraceptive or a copper IUD, or use of Depo-Provera within the last 120 days
- 6. Currently breastfeeding or having breastfed an infant in the last two months, or planning to breastfeed during the course of the study
- 7. Significant gynecological abnormalities (including abnormal vaginal bleeding or excessive vaginal discharge)
- 8. Either device does not appropriately fit volunteer, as determined by clinician
- 9. Inability of the volunteer to insert, position, and/or remove either device, even with assistance
- 10. History of sensitivity/allergy to nonoxynol-9 or to silicone or any other component of Ovaprene™ or Caya, for either the volunteer or her male partner
- 11. In the last four months, either the volunteer or her male partner diagnosed with or treated for any STI or pelvic inflammatory disease. Note: Women or male partners with a history of genital herpes or condylomata who have been asymptomatic for at least six months may be considered for eligibility
- 12. Positive test for Trichomonas vaginalis, Neisseria gonorrhea, Chlamydia trachomatis, or HIV
- 13. Deep epithelial genital findings such as abrasions, ulcerations, and lacerations, or vesicles suspicious for a sexually transmitted infection
- 14. Chronic or acute vulvar or vaginal symptoms (pain, irritation, spotting, etc.)
- 15. Known current drug or alcohol abuse which could impact study compliance. (This is defined as any illicit drug use or more than 15 alcoholic drinks per week)
- 16. Participation in any other investigational trial within the last 30 days or planned participation in any other investigational trial during the study
- 17. History of gynecological procedures (including genital piercing) on the external genitalia, vagina or cervix within the last 14 days
- 18. Abnormal finding on laboratory or physical examination or a social or medical condition in either the volunteer or her male partner which, in the opinion of the investigator, would make participation in the study unsafe or would complicate interpretation of data
- 19. Nugent score greater than or equal to 7
- 20. Systemic use in the last two weeks or anticipated use during the study of antibiotics (other than those used to treat UTI, vaginal candidiasis, or BV diagnosed at Visit 1, or to treat UTI or vaginal candidiasis after Visit 1) or topical antivirals (e.g., acyclovir or valacyclovir). Note: Participants should avoid non-steroidal anti-inflammatory drugs (NSAIDs) and Tylenol except for occasional use, as in treatment of headaches or dysmenorrhea.
- 21. Grade 2 or higher abnormality per the March 2017 update of the Division of AIDS (DAIDS), National Institute of Allergy and Infectious Disease (NIAID) Table for Grading of the Severity of Adverse Events or clinically significant lab abnormalities as determined by the investigator (see Section 13.5 for link to DAIDS table)
- 22. Inability to achieve adequate cervical mucus in two attempts at the baseline cycle
- 23. Inadequate sperm in endocervical aspirate during baseline testing without any device, despite adequate mucus and presence of sperm in vaginal pool

Version: 06.00 (FINAL) Date: June 13, 2019

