#### 9.1.2 Procedures:

- The study and informed consent form will be reviewed and all volunteer questions will be answered. If the volunteer wishes to participate and meets the preliminary study criteria, she will be asked to review and sign an informed consent form. The PI or designee will sign the form and provide a copy to the participant. Once the consent form is signed, the participant will be considered in screening.
- The male partner will be required to sign an informed consent form prior to the start of the female participant's menstrual period in the Baseline PCT Cycle.
- An interview will be conducted to obtain a medical/obstetrical history and demographic information.
- Height and weight will be measured.
- A urine specimen will be obtained for a urine pregnancy test to confirm that the
  participant is not pregnant and to perform a dipstick urinalysis if the participant is
  symptomatic for a urinary tract infection (UTI).
- An HIV test will be performed for female participants, along with appropriate counseling and/or referral. The male partner will be offered HIV testing and counseling.
- Blood will be drawn for a complete blood count (CBC), serum chemistries, and serum ferritin.
- A directed physical exam will be performed if the history is significant for a medical condition.
- A pelvic exam will be performed, including:

Version: 06.00 (FINAL) Date: June 13, 2019

- Signs of irritation of the external genitalia, cervix, and vagina, as observed with the naked eye, will be noted.
- o A colposcopic exam will be completed.b
- o Vaginal sample(s) will be collected for wet mount, vaginal pH, and Nugent score.
- o Specimens for *Trichomonas vaginalis, Neisseria gonorrhea* and *Chlamydia trachomatis* will be collected.
- o A Pap test will be performed, if necessary, consistent with standard medical practice as outlined in the Study Procedures Manual.
- UTI, vaginal candidiasis, and BV will be treated, preferably with oral medication. If the participant is otherwise eligible, she will continue in the study.

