#### 10.2 CONCOMITANT MEDICATIONS

Prohibited medications include use of intravaginal products at times specified in the protocol, as well as all hormonal contraceptives and treatment for BV and STIs. All concomitant medications will be recorded on CRFs.

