**Table 14: Endpoint Evaluations** 

	Goal	Baseline	Compared with
Changes in CBC,* chemistries,* and ferritin, colposcopy*	Assess effect of device on these endpoints after one cycle of use in the absence of sex, compared with before insertion	OS1	OS5
Nugent score,* vaginal microflora, vaginal antibacterial	Assess effect of device on these endpoints over one cycle, in the absence of sex, compared with before insertion	OS1	OS2, OS3, OS4, OS5
activity, and soluble markers	Assess effect of device on these endpoints after the device has been in place for one cycle, with multiple acts of sex up until 72 hours before the last visit, compared with before insertion	OP1	OP5
Vaginal antibacterial activity and soluble markers of inflammation	Assess effect of device insertion on these markers, in the absence of sex	BP1	OS1 after device insertion Baseline sample cannot be collected before device insertion at this visit because collection technique (vaginal lavage) is likely to affect subsequent samples taken at this visit.
	Assess effect of device on these markers after sex, compared with after sex with no device in place	BP2	OP3
	Assess effect of device on these markers after sex, compared with before sex	OP1	OP3

\* Also done at Visit 1 to establish eligibility

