characteristics and sperm  Cervical mucus by pipette - ferrous		Х	Х		Х	Х							Х	Х			Х
gluconate									Х		Х	Х	Х	Х		Х	х
Replace Ovaprene if displaced									X		X		X	X		X	X
Vaginal lavage - antibacterial activity,											7.			,			
soluble markers		Χ	X 				$X^{11}$	Χ	Х	Х	Х	Х		X 		Х	Х
Remove Ovaprene - swab for staph																	
aureus and store											Χ					Χ	Χ
Colpo exam of cervix under																	
magnification	Х						Χ				Χ	Χ				Χ	Х
Pap Test 	Х									1							
GC/CT if using cervical specimens 	Χ																Χ
Colpo exam of fornices and of vagina																	
(latter while removing speculum)	Х						Х				Х	Х				Χ	Х
Ovaprene Fit Test				Χ													
Caya Fit Test	Х																Х
Insert Ovaprene 							Χ					Χ					Χ
Remove Caya						Χ											Χ
Dispense Caya					Χ												
Explain Trials.ai	Х																
Dispense OPK Kit	Χ			Χ				Χ				Х				Χ	Χ
Dispense condoms	Χ			Χ							0					0	Χ

<sup>1 Medical and Obstetrical history will include contraceptive and gynecological history also.

Version: 06.00 (FINAL) Date: June 13, 2019

<sup>2 A physical exam will be performed if the history is significant for a medical condition. The directed physical exam can be performed at any visit.

<sup>3 HIV testing will be performed on all female participants. HIV testing is available for the male partners, if requested.

<sup>4 Urinalysis is only required if participant is symptomatic for UTI. Treat UTI with oral meds. If Visit 1, continue participant. If after Visit 1, reschedule visit.

<sup>5 The pelvic exam at every visit should look for signs of irritation of the external genitalia, cervix and vagina, as seen with the naked eye. A Pap Test will be performed at Visit 1, if necessary, consistent with the standard medical practice as outlined in the study manual.

<sup>6 **STI**: treat with oral meds and do not continue participant.

<sup>7 **Candidiasis**: treat with oral meds. If Visit 1, continue participant. If after Visit 1, reschedule visit. **BV**: treat with oral meds. If diagnosed at Visit 1, continue participant. If diagnosed after Visit 1, do not continue participant.

<sup>8 EVMS only: Cervical mucus pH will also be tested at 0.5, 1, 2, 4, and 6 hour time points, if possible.

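### The protocol gives conflicting rules for BV and a Nugent score of 7 or more at Visit 1, so sites can reach opposite enrolment decisions; the analysis effect is confined mainly to the BP1/BP2 marker baselines

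*Protocol*

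**What the plan says.** Protocol section 8 requires that a volunteer meet "none of the exclusion criteria prior to enrollment", and places enrolment at successful completion of the baseline PCT cycle. Exclusion 19 is a "Nugent score greater than or equal to 7", with no visit named, no retest and no exception after treatment. Table 14 marks the Nugent score as "Also done at Visit 1 to establish eligibility". In Appendix 1 the score is scheduled at screening and next at OS1, which is after enrolment at BP3.

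Four other places deal with BV or its treatment:

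- 9.1.2 (Visit 1): "UTI, vaginal candidiasis, and BV will be treated, preferably with oral medication. If the participant is otherwise eligible, she will continue in the study".
- 8.2 (20) bars recent or anticipated antibiotics "other than those used to treat UTI, vaginal candidiasis, or BV diagnosed at Visit 1" (it also makes an allowance for UTI and candidiasis after Visit 1).
- Appendix 1, footnote 7, attached to the wet-mount row: "If diagnosed at Visit 1, continue participant". BV diagnosed later means she does not continue.
- 10.2 lists as prohibited the use of intravaginal products at specified times, "as well as all hormonal contraceptives and treatment for BV and STIs".

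The analysis baselines are in Protocol Table 14 and SAP 3.7.6. Nugent score changes are taken from OS1 and from OP1. Antibacterial activity and soluble markers use those baselines too, and are also compared from BP1 to OS1 and from BP2 to OP3.

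**The concern.** Eligibility should not depend on which page of the protocol a site opens. Here a woman with BV and a high Nugent score at the same visit is barred by one rule and continued by another. The treatment that would allow her to continue is permitted in one section and prohibited in a second. No passage says how BV is to be diagnosed at Visit 1, or whether a score of 7 or more can be cleared by treatment.

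The situation can arise in ordinary practice. At Visit 1, "Vaginal sample(s) will be collected for wet mount, vaginal pH, and Nugent score", and 9.1.2 lets a woman move on while laboratory results are pending. A site may treat and continue her on the wet mount and then receive a score of 7 or more. SAP 3.3 tabulates failure to meet eligibility criteria as a deviation type, so whether she is counted there also depends on the reading.

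For the analysis, the question is whether a sample labelled as a no-device baseline was taken soon after BV was diagnosed and treated. If it was, part of the later change could reflect recovery from BV or its treatment and not the device. The study has no concurrent untreated group that would separate the two.

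**Working it through.** The plan states no figure to reproduce. The check is a comparison of the rules, followed by arithmetic on visit timing.

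**1. The rules applied to each kind of woman at Visit 1**

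| Visit 1 finding | Exclusion 19 | Appendix 1 footnote 7 | 9.1.2 | 10.2, if treated and continued |
|---|---|---|---|---|
| BV, score below 7 | does not bar | continue | continue if nothing else bars her | breached |
| BV, score 7 or more | bars | continue | depends on what otherwise eligible covers | breached |

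Exclusion 20 does not bar the antibiotics in either row. The first row has one conflict (10.2 against 9.1.2, exclusion 20 and footnote 7). The second row has that conflict and a second one over enrolment itself.

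**2. Time from Visit 1 to BP1**

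9.1.2 (footnote) allows the baseline PCT cycle to be completed in the same menstrual cycle as Visit 1 if Visit 1 falls before day 10. The latest such day is day 9. In the protocol's illustrative 28-day cycle (Table 6) the high ovulation-kit result is on day 13, and BP1 is on that day or the next, so day 13-14.

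- 13 − 9 = 4 days; 14 − 9 = 5 days.
- BP2 follows within about 27 hours of BP1.

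BP1 and BP2 are the baselines for the BP1-to-OS1 and BP2-to-OP3 comparisons of antibacterial activity and soluble markers. A microflora sample that 9.2.1 calls baseline is also taken at BP1.

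**3. Time from Visit 1 to OS1, same shortest path**

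Inputs: cycle length L = 24-35 days (inclusion 3); Visit 1 on day 9 of the baseline cycle; one full Caya cycle; OS1 on about day 6 of the next cycle (9.4.1).

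Interval = (L − 9) + L + 6 = 2L − 3.

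- L = 24: 45 days.
- L = 28: 53 days.
- L = 35: 67 days.

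The first OP1 comes one further cycle later, 3L − 3, which is 69 days at L = 24.

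**4. Weight of one woman**

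With about 25 completers, 1/25 = 4%. As illustration only, 1 to 5 such women would be 4% to 20% of that set. The documents contain no figure for BV at Visit 1.

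**The case against.** The strongest reply is that 9.1.2 already contains the answer. A treated woman continues only if otherwise eligible, and section 8 requires that no exclusion be met. On that reading exclusion 19 stays in force and only BV with a score below 7 continues. Footnote 7 belongs to the wet-mount row, and the documents nowhere equate BV with a score of 7 or more. This is a reasonable reading, so a reader should not infer that the rules clash for every woman with BV. It does not settle the matter: the protocol does not say that the phrase includes exclusion 19, and footnote 7 omits the phrase.

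On 10.2, one can say that a one-sentence general list yields to three specific provisions. That is probably how many sites would act. But 10.2 has no Visit 1 exception and does not say that it applies only later, so the texts still disagree.

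A repeat score is also possible: Appendix 1 marks the Nugent score in the unscheduled-visit column, and eligibility is judged up to enrolment. No passage calls for that repeat or says that it would override the Visit 1 result.

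Three stronger inferences are tempting and are not supported:

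- *That treated BV contaminates the Nugent and microflora change baselines.* Table 14 measures those changes from OS1 and OP1, at least about 45 days after Visit 1. BV diagnosed in between leads to non-continuation (9.2.1, footnote 7).
- *That recurrence would generally pass for a device effect.* A recurrence diagnosed before OS1 removes the woman before any Ovaprene cycle. Only a later one could be mistaken for an effect of the device.
- *That a number of affected women can be given by applying an assumed prevalence to the 45 enrolled.* The enrolment conflict acts on screened women and needs a score of 7 or more as well as BV. Exclusions 7 and 14 (gynecological abnormalities, vulvar or vaginal symptoms) would remove some women with BV. A count out of 45 also cannot be set against 25 completers.

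Finally, the safety analyses are descriptive, and because medications and all collected data are listed, treated women could be identified afterwards. That limits the harm and makes the remedy easier. It does not resolve who may be enrolled.

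**Conclusion.** The concern holds in a limited form. For a woman with BV and a Nugent score of 7 or more at Visit 1, the protocol supports both enrolment and screen failure. For any woman treated for BV at Visit 1 and continued, 10.2 is breached as written.

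The analysis consequence is modest. It concerns descriptive secondary safety endpoints, chiefly the BP1-to-OS1 and BP2-to-OP3 changes in antibacterial activity and soluble markers, plus the BP1 microflora sample. No effect on the primary PCT endpoint is shown. The 4-5 day interval assumes Visit 1 on day 9 and the protocol's illustrative 28-day cycle; the 45-day interval assumes 24-day cycles and OS1 on day 6. The number of women is unknown, and the documents do not say how these markers respond to BV treatment, so neither the size nor the direction of any distortion can be stated. Each such woman would be 4% of about 25 completers. The amendment is worth making because it is cheap and because eligibility should have one answer.

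**What to change.** Reconcile Protocol 8.2 (19), 8.2 (20), 9.1.2, Appendix 1 footnote 7 and 10.2 so that a single rule decides. The text should state whether exclusion 19 applies to a Visit 1 score of 7 or more when BV is diagnosed at that visit, and footnote 7 and 10.2 should then agree with it. Which rule to adopt is a clinical decision for the sponsor and investigators; this review does not choose one.

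If women with BV at Visit 1 can be enrolled under the rule adopted, or have already been enrolled, flag them in the analysis data and repeat SAP Table 14.3.5.9 without them, for the BP1-to-OS1 and BP2-to-OP3 changes. Repeating Table 14.3.5.8 (Nugent scores) is optional, given the longer interval to its baselines.

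The cost is a wording amendment, a flag built from Visit 1 findings and medication records already collected, and one or two extra descriptive tables on a slightly smaller set. No new visit or sample is needed.
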